2.3 Study design

Statistical Analysis Plan (SAP) for Clinical Study AP-017

This is a Phase II randomized, double-blinded, placebo-controlled study to evaluate the safety and efficacy of IV Ampion in participants with COVID-19 who require supplemental oxygen.

Participants will be randomized 1:1 to active or placebo using a random allocation sequence stratified by disease severity.

All subjects receiving test product will also receive the standard of care (SOC) for COVID-19, which includes:

- Oxygen administration to maintain oxygen saturation of 90% or greater.
- Nursing physical that may include review of neurological; pulmonary; cardiac; gastrointestinal; and urinary assessment at least daily during treatment.
- Vital monitoring (heart rate, blood pressure, temperature, respiratory rate, SpO2) at least daily during treatment.
- Telemetry monitoring to evaluate heart rhythm and rate.
- Diet as tolerated to satisfy nutritional needs.
- Treatments for COVID-19 symptoms including antibiotics, cough suppressants/expectorants, anti-coagulants, fever reducers/pain killers, anti-nausea drugs, and/or bronchodilators.
- Treatments for COVID-19 as approved by the FDA including expanded access, emergency, or compassionate use (i.e., remdesivir, dexamethasone).
- Medications will be recorded as concomitant medication, tabulated, and compared among groups.

The clinical effects, safety, and tolerability of treatment will be evaluated from baseline to Day 28 and through Day 60. Evaluations at screening and during the 5-day treatment occur in person. Evaluations after the 5-day treatment to the end of the study (days 7 to 60) will typically occur via telephone contact unless the patient is in an inpatient setting.

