2.4 Sample Size

The trial is designed to enroll up to approximately 200 patients across two treatment arms (active or control), with 100 subjects per arm, randomized 1:1 using a random allocation sequence stratified by COVID-19 disease severity (severe or critical). An interim analysis of the data is planned after 30 subjects (approximately n=15 subjects per arm) to evaluate the relative effect. At the interim analysis, the sample size may be re-estimated to determine the additional number of patients required for adequate power to meet the chosen effect size for the primary endpoint.

The number of participants is selected based on the effects observed for the primary endpoint, prevention of need for mechanical ventilation or death prior to day 28. A study recently reported in Lancet Respiratory Medicine with 243 hospitalized patients receiving the placebo for COVID-19 found 22% did not achieve day 28 ventilation-free survival (Lancet Respir Med 2021; [https://doi.org/10.1016/S2213-2600\(21\)00494-X](https://doi.org/10.1016/S2213-2600(21)00494-X)). In the AP-014 study, a lower rate (8%) was observed for subjects receiving inhaled Ampion. Assuming the same proportions (8% for Ampion and 22% for control) by Day 28, with 100 subjects per group, a two-sided 5% significance level, and using a z-test with unpooled variances, then under binomial enumeration the power to detect this difference is about 81.3%.

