3. STUDY ENDPOINTS AND ANALYSES

Statistical Analysis Plan (SAP) for Clinical Study AP-017

3.1 Primary Endpoint:

The primary endpoint assesses the effect of Ampion compared to placebo on prevention of need for mechanical ventilation or death prior to day 28. This is measured as the occurrence of mechanical ventilation or death by Day 28.

Let π_A and π_S represent the rate of this outcome for Ampion and control during the first 28 days after randomization. Then it is desired to demonstrate that the mechanical ventilation and death rate for Ampion is different than the corresponding rate for the control. Formally, this is presented as:

$$H_0: \pi_A = \pi_S \text{ versus } H_A: \pi_A \neq \pi_S$$

This will be tested utilizing the appropriate chi-square test or Fisher's exact test utilizing PROC FREQ with the EXACT option, if necessary.

Also, the median time to mechanical ventilation or death will be tested for difference between the two groups via the log-rank test. The test will be performed using PROC LIFETEST. The time to event distributions in each group will be estimated using the method of Kaplan and Meier.

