3.2 Secondary Endpoints

3.2.1 Change in ordinal scale from baseline through Day 7, Day 14 and Day 28.

The hypotheses to be tested are:

$$H_0: \mu_A = \mu_S \text{ versus } H_A: \mu_A \neq \mu_S$$

Where μ_A and μ_S represent the ordinal scale shift through day 7, 14, and 28 for Ampion and Placebo after randomization. The difference between Ampion and Placebo with respect to the change from baseline at day 7, 14, and 28 will be tested utilizing a Wilcoxon rank-sum test via PROC NPAR1WAY. To assess any potential time trends, an exploratory repeated measures analysis of variance will be performed with terms for treatment, time and the interaction between the two. This will be done utilizing PROC GLM with the REPEATED option.

3.2.2 Change in NEWS2 score from baseline through Day 7, or discharge if earlier.

The hypotheses to be tested are:

$$H_0: \mu_A = \mu_S \text{ versus } H_A: \mu_A \neq \mu_S$$

Where μ_A and μ_S represent the mean change from baseline in the NEWS2 score assessment through day 7 for Ampion and Placebo after randomization. The difference between Ampion and Placebo with respect to the change from baseline at day 7, or discharge if earlier, will be tested utilizing a Wilcoxon rank-sum test via PROC NPAR1WAY. To assess any potential time trends an exploratory repeated measures analysis of variance will be performed with terms for treatment, time and the interaction between the two. This will be done utilizing PROC GLM with the REPEATED option.

3.2.3 Percentage of participants who progress to respiratory failure by Day 28.

The hypotheses to be tested are:

$$H_0: \pi_A = \pi_S \text{ versus } H_A: \pi_A \neq \pi_S$$

Statistical Analysis Plan (SAP) for Clinical Study AP-017

Let π_A and π_S represent the percentage of patients who have respiratory failure for Ampion and control during the first 28 days after randomization.

This difference will be tested utilizing the appropriate chi-square test or Fisher's exact test utilizing PROC FREQ with the EXACT option, if needed.

Also, the median time to respiratory failure will be tested for difference between the two groups via the log-rank test. The log-rank test will be performed using PROC LIFETEST; and the estimation of the time-to-event distributions will be performed using the method of Kaplan and Meier.

3.2.4 Percentage of participants who require Intensive Care Unit (ICU) admission by Day 28; ICU-free days through Day 28; ICU length of stay (LOS) from ICU admission to discharge.

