6. INTERIM ANALYSIS AND EARLY STOPPING GUIDELINES

6.1 Interim Analysis

This trial is designed to enroll up to approximately 200 subjects, randomized to active or control, following an equal allocation to treatment arms. An interim analysis of the data is planned after 30 subjects (approximately n=15 subjects per arm) to evaluate the relative treatment effect.

The interim analysis will be conducted on the primary and secondary endpoint data at an alpha level of 0.001 and thus the overall alpha level for the final test will be performed at approximately $\alpha=0.049$ instead of $\alpha=0.05$.

At the interim analysis, the sample size may be re-estimated to include additional subjects up to a total of 300 subjects to attain adequate power beyond the sample size of 200 originally calculated. This evaluation will be based on the methodology suggested by Gould et al. (Gould AL. Interim analyses for monitoring clinical trials that do not materially affect the type I error rate. Stat Med 1992; 11(1): 55-66) Let σ be the pooled rate of this study endpoint in the two arms, i.e. $\sigma=(p_{placebo}+p_{Ampion})/2$, where p is the incidence of the primary study endpoint in the respective groups. Let σ^* be the same value, but based on some assumed rates for these values from the beginning of the trial. Then the following sample size multiplier is determined:

$$f = [\sigma(1-\sigma)]/\sigma^*(1-\sigma^*)$$

If f is greater than 1, then the new sample size, n_1 , is determined as $f \times n$, where n is the original sample size (per group) of 100. If f is less than one, then the study will continue as originally envisioned.

The sponsor reserves the right to alter the final sample size if the assumptions of the rates of the primary endpoint are not satisfied at this interim analysis.

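### SAP 3.1 presents the log-rank as a test of median event time, which it is not and which the planned rates would leave unreached by Day 28; no between-arm estimate is specified for the primary endpoint

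*SAP*

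**What the plan says.** SAP 3.1 defines the primary endpoint as occurrence of mechanical ventilation or death by Day 28. It states one formal hypothesis, equality of the two proportions, and tests it by chi-square or Fisher's exact test. It then adds that "the median time to mechanical ventilation or death will be tested for difference between the two groups via the log-rank test", with Kaplan-Meier estimation in each group.

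SAP 3.2.3 uses the same construction for a secondary endpoint: "the median time to respiratory failure will be tested for difference between the two groups via the log-rank test".

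The sample size in SAP 2.4 rests on proportions: "Assuming the same proportions (8% for Ampion and 22% for control) by Day 28", "with 100 subjects per group, a two-sided 5% significance level". Protocol 9.4.1 has only the 2x2 test for the primary endpoint. SAP 9, which lists changes from the protocol, does not mention the log-rank test.

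On estimation:
- Protocol 9.3 plans counts, percentages and 95% confidence intervals for categorical data.
- Protocol 9.4.2 says the efficacy endpoints will be used to estimate the treatment effect. It names only descriptive statistics with 95% intervals, presented by arm.
- SAP 8.1 gives categorical variables counts and percentages, and attaches a 95% interval only to change from baseline.
- SAP table 10.2.1 is a summary of ventilation or mortality.

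Neither document names a risk difference, risk ratio, hazard ratio or Kaplan-Meier difference for the primary endpoint.

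**The concern.** The sentence in SAP 3.1 has two faults. The quantity it names cannot be estimated at the rates the trial was planned on, because the median is the time at which half of an arm has had the event. And the test it names does not address that quantity: two arms can have equal medians, or none, and still differ clearly on the log-rank test.

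The practical consequence is in the reporting. The median is the only summary that the SAP attaches to the time-to-event comparison. If it is not reached in either arm, what remains is a p-value. The SAP also specifies no between-arm estimate for the Day 28 proportion. SAP 2 says the trial's data are to inform decisions on clinical development, and for that the size of the effect and its uncertainty matter at least as much as the p-value. If the contrast and interval method are chosen after unblinding, that choice is open to the criticism that it was made with the results in view.

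**Working it through.** **Inputs.** Event rates by Day 28 of 8% (Ampion) and 22% (control), 100 patients per arm and two-sided 5%, all from SAP 2.4; final alpha of about 0.049 from SAP 6.1; end of study at Day 60 from SAP 4.7.

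**The plan's own figure.** Enumerating two Binomial(100, p) arms with the unpooled z-test at two-sided 0.05 gives 81.28% power, against the stated 81.3%. It reproduces, so the inputs are read correctly.

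**Is a median reached by Day 28?** Planned event-free proportions are 1 − 0.08 = 0.92 and 1 − 0.22 = 0.78, both well above 0.50. With complete follow-up to Day 28, a median requires at least 50 events among 100 patients:
- Control: P(X ≥ 50 | 100, 0.22) = 7.4 × 10⁻¹⁰.
- Ampion: P(X ≥ 50 | 100, 0.08) = 2.4 × 10⁻²⁸.

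**Would following to Day 60 help?** Assume a constant hazard, h = −ln(1 − p)/28, with median ln 2/h.
- Control: h = 0.2485/28 = 0.00887 per day, median about day 78.
- Ampion: h = 0.0834/28 = 0.00298 per day, median about day 233.

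Both fall after Day 60. Cumulative risk at Day 60 would be 1 − 0.78^(60/28) = 41% and 1 − 0.92^(60/28) = 16%.

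**Sensitivity to the planned rate.** The chance that the control arm reaches its median by Day 28:

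| True control rate | P(≥ 50 of 100 events) |
|---|---|
| 22% | 7.4 × 10⁻¹⁰ |
| 30% | 0.002% |
| 40% | 2.7% |
| 45% | 18% |
| 50% | 54% |

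**Is the log-rank test itself sound?** Under proportional hazards the planned rates imply HR = ln(0.92)/ln(0.78) = 0.0834/0.2485 = 0.336. With 8 + 22 = 30 events, Schoenfeld's formula gives power Φ(√(30/4) × |ln 0.336| − z), which is 84.9% at 0.05 and 84.7% at 0.049. The test works; its label is wrong.

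**Does having two tests cost type I error?** With 15% events in both arms, the average of 8% and 22%, and 100 per arm, 20,000 simulated trials at 0.049 gave rejection rates of 4.8% (chi-square), 4.7% (log-rank) and 5.0% (either). The cost is about 0.2 points.

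**What can be estimated at the planned counts (8/100 and 22/100)?**
- Risk difference: 22% − 8% = 14 points. The Wilson limits are 15.0% to 31.1% (control) and 4.1% to 15.0% (Ampion). The Newcombe limits are 14 − √(7.0² + 7.0²) = 4.1 and 14 + √(9.1² + 3.9²) = 23.9.
- Hazard ratio: 0.336, SE of the log about √(1/8 + 1/22) = 0.413, so the 95% CI is exp(ln 0.336 ± 1.96 × 0.413) = 0.15 to 0.75.

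**The case against.** A reader might infer that the trial will end with no effect size for its main outcome. The documents do not support that. The primary endpoint is a proportion. Percentages by arm are planned, with 95% intervals under protocol 9.3, and Kaplan-Meier curves are planned in each group. A risk difference is one subtraction away, and protocol 9.4.2 does speak of estimating the treatment effect, though under the secondary endpoints. What stands is narrower: no contrast, and no interval for it, is specified in advance.

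A reader might also infer that it is unclear which test decides, or that alpha is spent twice. The 2x2 test is evidently primary. It has the only formal hypothesis in SAP 3.1, it is the only primary test in protocol 9.4.1, and the sample size is based on proportions. The log-rank is introduced as an addition and is assigned no alpha. Even if both were used, the error cost is negligible. An explicit statement would still help, but its absence is minor.

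The unreached median depends on the planned rates. Protocol 4.4 admits patients already on endotracheal ventilation to the critical stratum, so the observed rate could differ from 22%. It would need to approach 50% before a control median became likely.

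For SAP 3.2.3 the argument about an unreachable median does not carry over. No respiratory-failure rate is given. The endpoint includes non-invasive ventilation, and protocol 5.2 adds high-flow oxygen; both are supports that define the critical stratum, so incidence could be well above 22%. Only the mismatch between hypothesis and test carries over.

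**Conclusion.** The point holds in this form. The log-rank test is described as a test of medians in SAP 3.1 and 3.2.3, and it is not one. For the primary endpoint, the median is also not reached by Day 28 in either arm if the planned 8% and 22% hold; a control median would remain unlikely at a true rate of 40% (2.7%). That result assumes the planned rates and 100 patients per arm with follow-up to Day 28. The extension to Day 60 also assumes a constant hazard.

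The log-rank p-value is valid, with about 85% power under proportional hazards, and the primary conclusion does not rest on it. The substantive loss is that no between-arm estimate with an interval is specified for the primary endpoint. This should be corrected before unblinding, but it does not threaten the validity of the primary test.

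**What to change.** 1. In SAP 3.1 and 3.2.3, replace the sentences on testing the median with: *the time-to-event distributions to Day 28 will be compared by a log-rank test stratified by severity, as a supportive analysis*. Stratification follows the randomization, which is by disease severity.
2. In SAP 3.1, state that the 2x2 test alone decides the primary endpoint.
3. Pre-specify the Day 28 risk difference with a 95% CI, naming the method (Newcombe or score). At the planned counts this is 14 points, about 4 to 24.
4. Accompany the log-rank with a severity-stratified Cox hazard ratio and 95% CI. At the planned rates under proportional hazards this is about 0.34; with some 30 events the interval is wide, roughly 0.15 to 0.75.

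A separate Kaplan-Meier difference at Day 28 is optional. The cost is a few lines in the SAP and one more row in table 10.2.1. No new data are needed, and the sample size and primary test are unchanged.

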3.2 Secondary Endpoints

3.2.1 Change in ordinal scale from baseline through Day 7, Day 14 and Day 28.

The hypotheses to be tested are:

$$H_0: \mu_A = \mu_S \text{ versus } H_A: \mu_A \neq \mu_S$$

Where μ_A and μ_S represent the ordinal scale shift through day 7, 14, and 28 for Ampion and Placebo after randomization. The difference between Ampion and Placebo with respect to the change from baseline at day 7, 14, and 28 will be tested utilizing a Wilcoxon rank-sum test via PROC NPAR1WAY. To assess any potential time trends, an exploratory repeated measures analysis of variance will be performed with terms for treatment, time and the interaction between the two. This will be done utilizing PROC GLM with the REPEATED option.

3.2.2 Change in NEWS2 score from baseline through Day 7, or discharge if earlier.

The hypotheses to be tested are:

$$H_0: \mu_A = \mu_S \text{ versus } H_A: \mu_A \neq \mu_S$$

Where μ_A and μ_S represent the mean change from baseline in the NEWS2 score assessment through day 7 for Ampion and Placebo after randomization. The difference between Ampion and Placebo with respect to the change from baseline at day 7, or discharge if earlier, will be tested utilizing a Wilcoxon rank-sum test via PROC NPAR1WAY. To assess any potential time trends an exploratory repeated measures analysis of variance will be performed with terms for treatment, time and the interaction between the two. This will be done utilizing PROC GLM with the REPEATED option.

3.2.3 Percentage of participants who progress to respiratory failure by Day 28.

The hypotheses to be tested are:

$$H_0: \pi_A = \pi_S \text{ versus } H_A: \pi_A \neq \pi_S$$

Statistical Analysis Plan (SAP) for Clinical Study AP-017

Let π_A and π_S represent the percentage of patients who have respiratory failure for Ampion and control during the first 28 days after randomization.

This difference will be tested utilizing the appropriate chi-square test or Fisher's exact test utilizing PROC FREQ with the EXACT option, if needed.

Also, the median time to respiratory failure will be tested for difference between the two groups via the log-rank test. The log-rank test will be performed using PROC LIFETEST; and the estimation of the time-to-event distributions will be performed using the method of Kaplan and Meier.

3.2.4 Percentage of participants who require Intensive Care Unit (ICU) admission by Day 28; ICU-free days through Day 28; ICU length of stay (LOS) from ICU admission to discharge.

There are two endpoints in this set. Hypotheses about both will be tested independently. The first hypothesis about the percentage of patients who are admitted to the ICU involves all patients. The second hypothesis involves only patients who are admitted to the ICU. Since it is not known how many many patients will be admitted to the ICU, the testing of the second hypothesis will be considered exploratory and not part of the hierachial testing scheme.

The first hypotheses to be tested is:

$$H_0: \pi_A = \pi_S \text{ versus } H_A: \pi_A \neq \pi_S$$

Where π_A and π_S represent the percentage of patients who are admitted to the ICU for Ampion and Placebo during the first 28 days after randomization. The difference between Ampion and Placebo will be tested via an appropriate chi-square test or Fisher's exact test utilizing PROC FREQ with the EXACT option, if needed.

The second hypothesis to be tested is:

$$H_0: \text{Median}_A = \text{Median}_S \text{ versus } H_A: \text{Median}_A \neq \text{Median}_S$$

Where Median_A and Median_S are the median ICU length of stay for the Ampion and placebo groups. Assuming there is no censoring, this will be tested using the Wilcoxon rank sum test via PROC NPAR1WAY. If censoring occurs, e.g., death, then the log rank test will be used based on PROC LIFETEST.

3.2.5 Modulation of cytokine levels from baseline to Day 5.

The hypotheses to be tested are:

$$H_0: \mu_A = \mu_S \text{ versus } H_A: \mu_A \neq \mu_S$$

Where μ_A and μ_S represent the mean percent change from baseline in the cytokine levels at day 5 for Ampion and Placebo after randomization. The difference between Ampion and Placebo with respect to the percent change from baseline at day 5 will be tested utilizing a two sample t-test via PROC TTEST. To assess any potential time trends an exploratory repeated measures analysis of variance will be performed with terms for treatment, time and the interaction of the two. This will be done utilizing PROC GLM with the REPEATED option.

Statistical Analysis Plan (SAP) for Clinical Study AP-017

3.2.6 Hospital length of stay.

The hypotheses to be tested are:

$$H_0: \text{Median}_A = \text{Median}_S \text{ versus } H_A: \text{Median}_A \neq \text{Median}_S$$

Where Median_A and Median_S are the median hospital length of stay for the Ampion and placebo groups. Assuming there is no censoring, this will be tested using the Wilcoxon rank sum test via PROC NPAR1WAY. If censoring occurs, e.g., death, then the log rank test will be used based on PROC LIFETEST.

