4.4 Inclusion Criteria

Patients should fulfill all the following inclusion criteria:

1. Male or female, ≥ 18 years old.
2. Diagnosed with COVID-19, as evaluated by laboratory diagnostic test or diagnosis based on radiological clinical findings.
3. Baseline severity categorization of severe or critical COVID-19 infection per FDA Guidance for developing drugs and biological products for COVID-19 (February 2021):
 - a) Severe COVID-19:
 - Symptoms suggestive of severe systemic illness with COVID-19, which could include shortness of breath or respiratory distress
 - Clinical signs indicative of severe systemic illness with COVID-19, such as respiratory rate ≥ 30 per minute, heart rate ≥ 125 per minute, $\text{SpO}_2 \leq 93\%$ on room air at sea level ($\text{SpO}_2 \leq 90\%$ at altitude) or $\text{PaO}_2/\text{FiO}_2 \leq 300$
 - b) Critical COVID-19:
 - Oxygen delivered by high-flow nasal cannula (heated, humidified, oxygen delivered via reinforced cannula at flow rates > 20 L/min with fraction of oxygen ≥ 0.5) or
 - Non-invasive mechanical or endotracheal mechanical ventilation
4. Informed consent obtained from the patient or the patient's legal representative.

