4.5 Exclusion Criteria

Patients fulfilling one or more of the following criteria may not be enrolled in the study:

1. As a result of the medical review and screening investigation, the Principal Investigator considers the patient unfit for the study and/or progression to death is imminent and inevitable irrespective of the provision of treatments.
2. Clinical diagnosis of respiratory failure (therapy not able to be administered in setting of resource limitation).
3. Shock defined by systolic blood pressure <90 mm Hg, or diastolic blood pressure <60 mm Hg or requiring vasopressors. Vasopressor therapy is exclusionary if used to treat shock. Subjects receiving low dose vasopressors to maintain renal perfusion are eligible.
4. Multi-organ dysfunction/failure.
5. Patient has severe chronic obstructive or restrictive pulmonary disease (COPD) (as defined by prior pulmonary function tests), chronic renal failure (only exclusionary if subject is currently on renal replacement therapy, i.e., subjects receiving peritoneal dialysis, hemodialysis, ultrafiltration are ineligible), or significant liver abnormality (e.g., cirrhosis, transplant, etc.).
6. Patient has chronic conditions requiring chemotherapy or immunosuppressive medication (only exclusionary if subject is currently receiving a high dose or therapy for transplantation, e.g., subjects receiving low dose inhaled or oral steroids for asthma are eligible).

7. A history of allergic reactions to human albumin (reaction to non-human albumin such as egg albumin is not an exclusion criterion) or ingredients in 5% human albumin (N-acetyltryptophan, sodium caprylate).
8. Prolonged QT interval.
9. Patient has known pregnancy or is currently breastfeeding.
10. Patient planning to become pregnant, or father a child, during the treatment and follow-up period and/or is not willing to remain abstinent or use contraception.
11. Participation in another clinical trial (not including treatments for COVID-19 as approved by the FDA through expanded access, emergency, or compassionate use), or participation in a trial such that enrollment in this study would fall within the time frame of the half-life of the other investigational product(s).

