0	No clinical or virological evidence of infection
1	No limitation of activities
2	Limitation of activities
3	Hospitalized, no oxygen
4	Hospitalized, oxygen by mask or nasal prongs
5	Hospitalized, non-invasive ventilation or high-flow oxygen
6	Hospitalized, mechanical ventilation
7	Hospitalized, ventilation + additional organ support – pressors, RRT, ECMO
8	Death

NEWS2 Score for Determining the Degree of Illness

The NEWS2 will be calculated using the oxygenation requirement (room air or supplemental oxygen), SpO2 level, and vitals (body temperature, respiratory rate, heart rate and blood pressure) collected during study visits. The NEWS2 score is recommended by the National Institute for Health and Care Excellence (“NICE”) for managing COVID-19 patients.

Adverse Events

Any documented adverse event. These include but are not limited to the following: cardiac injury, arrhythmia, septic shock, liver dysfunction, acute kidney injury, and multi-organ failure.

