For any variable, unless otherwise defined, baseline is the last assessment taken prior to the first study drug administration.

4.6 Change from Baseline:

The arithmetic difference between a post-baseline value and the baseline value:

Change from Baseline = (Post-baseline Value – Baseline Value)

Percentage Change from Baseline = [(Post-baseline Value – Baseline Value) / Baseline Value] x 100

4.7 End of Study:

End of study is at Day 60 unless terminated early.

4.8 Enrollment Date:

Enrollment date is the same as the randomization date and is designated Day 0.

4.9 Study Drug:

Study drug in this study is Ampion plus SOC or Placebo plus SOC.

4.10 Randomization Date:

Randomization date is the day the subject is assigned a randomization number on study Day 0.

4.11 Study Day 1:

Day 1 is defined as the first day that study drug is administered to the subject.

4.12 Study Day:

Day of treatment: study day = (visit date - date of Study Day 1 + 1)

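### The first efficacy endpoint in the secondary hierarchy is tested by a rank-sum test on ordinal change that uses neither severity nor baseline score as a stratum or covariate; this loses some power and ties or misorders a few deaths.

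*SAP*

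**What the plan says.** SAP 3.2.1 compares the arms "with respect to the change from baseline at day 7, 14, and 28 will be tested utilizing a Wilcoxon rank-sum test via PROC NPAR1WAY". A repeated measures analysis of variance is added as exploratory. The section names no stratum, no covariate and no separate rule for ranking death. SAP section 4 defines change as "The arithmetic difference between a post-baseline value and the baseline value".

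On the scale in Protocol 5.2, score 4 is oxygen by mask or prongs and 5 is high-flow oxygen or non-invasive ventilation. Score 6 is "Hospitalized, mechanical ventilation", 7 is "Hospitalized, ventilation + additional organ support" and 8 is death.

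SAP 2.4 describes patients as "randomized 1:1 using a random allocation sequence stratified by COVID-19 disease severity (severe or critical"). Both schedules of assessments record the ordinal score at Day 0. Protocol 9.3 and 9.4.2 use severity for efficacy only in descriptive summaries.

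On baseline scores, Protocol 4.4 lists "Non-invasive mechanical or endotracheal mechanical ventilation" within the critical category, while Protocol 4.5 excludes "Clinical diagnosis of respiratory failure (therapy not able to be administered in setting of resource limitation").

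SAP 8.6 tests the secondary endpoints in the order of SAP 3.2, so 3.2.1 is the first step after the primary endpoint.

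**The concern.** A rank-sum test on change ranks all 200 patients together, whatever their starting score. A fall or rise of two steps then counts the same from 4, 5 or 6, although the steps mean different things. The scale has a ceiling at 8, so the sicker a patient is at entry, the smaller the change that death can produce. The test can therefore treat a death as no worse, or even as better, than survival on a ventilator.

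Severity is also strongly prognostic and was used to randomise. Leaving it out of the test adds between-stratum variation to the comparison and costs power.

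At stake are the interpretability of the endpoint that opens the secondary hierarchy and some power at the step on which every later secondary claim depends.

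**Working it through.** **Planning figures.** The documents give no power or effect size for this endpoint. Their only power statement is for the primary endpoint (8% v 22%, 100 per arm, two-sided 5%, unpooled z-test): 81.3%. Exact binomial enumeration gives 81.28%, so it reproduces, but it says nothing about the ordinal test.

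**Step 1: ranking.** Change = later score − baseline score, with death = 8 and oxygen-requiring patients entering at 4 or above.

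| Patient who dies | Change | Survivors tied | Survivors ranked worse than the death |
|---|---|---|---|
| from 4 | 8 − 4 = +4 | none | none |
| from 5 | 8 − 5 = +3 | 4→7 | none |
| from 6 | 8 − 6 = +2 | 4→6, 5→7 | 4→7 (+3) |

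With entry scores 4 and 5 only, there are ties but no strict reversals. A strict reversal needs a patient at baseline 6. The recovery end has the same feature: 5→3 (still in hospital) and 4→2 (a category below the hospitalised ones) are both −2.

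**Step 2: within one baseline level.** If all patients in a stratum start at b, change = score − b. Subtracting a constant leaves ranks unchanged, so ranking change and ranking score are the same test there, and death is always last. The misordering comes only from comparisons across baseline levels.

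**Step 3: power.** Simulation of 200 patients, 1:1 within severity, two-sided 5%, 3,000 trials per row. All distributions are assumptions. Control Day 28 percentages for scores 1 to 8:

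- baseline 4: 45, 25, 8, 6, 3, 2, 2, 9
- baseline 5: 28, 22, 8, 7, 6, 5, 4, 20
- baseline 6: 10, 15, 6, 6, 5, 13, 10, 35

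The active arm is shifted by a common odds ratio of 0.5. Baseline 4 is taken as severe, 5 and 6 as critical. Power (%):

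| Baseline mix 4/5/6 (%) | Change, plain (SAP) | Change, van Elteren by severity | Score, van Elteren by baseline | Score, plain | Reversed pairs | Tied pairs |
|---|---|---|---|---|---|---|
| 80/15/5 | 71.1 | 73.2 | 72.8 | 70.9 | 0.21 | 0.64 |
| 65/25/10 | 71.6 | 74.0 | 74.3 | 69.6 | 0.29 | 0.93 |
| 50/30/20 | 71.4 | 75.3 | 75.7 | 69.1 | 0.37 | 1.15 |
| 50/10/40 | 70.7 | 74.5 | 74.9 | 64.1 | 0.64 | 1.00 |

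The last two columns are percentages of death-survivor pairs.

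Gain of van Elteren by baseline over the SAP test: 72.8 − 71.1 = 1.7; 74.3 − 71.6 = 2.7; 75.7 − 71.4 = 4.3; 74.9 − 70.7 = 4.2 points. Stratifying change by severity alone gives 2.1, 2.4, 3.9 and 3.8. Stratification therefore produces nearly all of the gain; replacing change by score adds almost nothing. The raw score without strata is no better and can be clearly worse.

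Other assumed distributions at alpha 0.049 agree. With entry scores 4 and 5 only, the plain test had 73.2–76.2% and the stratified test 74.5–78.4%. A further set gave 72–75% v 75–77%. Across all runs the gain is about 1 to 5 points.

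**Step 4: type I error.** With no effect, the SAP test rejected in 4.6–5.7% of trials and van Elteren by baseline in 4.7–5.2%. The simulation standard error is √(0.05 × 0.95 / 3000) = 0.4 points, so neither is inflated. Reversed pairs were then 0.3–0.9% and tied pairs 0.8–1.5%.

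**Step 5: model-based alternative.** In 502 trials with the 65/25/10 mix, power was 70.1% for the SAP test, 72.7% for van Elteren by baseline and 73.3% for a proportional-odds model adjusted for baseline score.

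**The case against.** A reader might infer that the test ignores the baseline score. It does not: subtraction puts baseline into every observation. What is missing is baseline or severity as a stratum or covariate.

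A reader might also infer that deaths will certainly rank above survivors. The documents do not settle that. Inclusion 3b names endotracheal ventilation, but exclusion 2 bars respiratory failure with a qualifier that is hard to interpret. The secondary endpoint list counts invasive and non-invasive ventilation as respiratory failure. Protocol 2.4.1 describes treating patients before they become critical, and the primary objective is to prevent ventilation. If nobody enters at 6, only ties remain.

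The effect is small in any case. The endpoint is secondary, SAP 8.6 treats it as supporting the primary, and every death by Day 28 already counts as a failure in the primary endpoint.

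Finally, replacing change by the score would redefine an endpoint that both documents call a change, and Protocol 10.3 requires a formal amendment for protocol changes. That objection stands against a wholesale switch, which Step 2 shows to be unnecessary. None of these points defends leaving the randomisation factor out of the test.

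**Conclusion.** The plain rank-sum test is valid but not the best available with the data already planned. Under the assumed distributions and an odds ratio of 0.5, omitting the stratum costs about 1 to 5 power points. The exact figure depends on the baseline mix and outcome distribution, which the documents do not give. Ties between some deaths and survivors follow from the scale and the definition of change whenever entry scores 4 and 5 both occur. Strict reversals depend on ventilated patients being enrolled, and the eligibility passages must be reconciled before anyone can say whether they will occur. Fewer than 1% of death-survivor pairs were reversed in the simulations.

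The documents do not support a claim of inflated type I error, or of any effect on the primary analysis. The point is a cheap improvement to an important secondary test, not a flaw that invalidates it.

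**What to change.** In SAP 3.2.1, replace the plain test with a van Elteren test at each of Days 7, 14 and 28, stratified by baseline ordinal score, with death scored 8. Say in advance how sparse levels are pooled within severity; at the least, stratify by severity. Pooling has a limit: if baselines 5 and 6 share a stratum and change is ranked, a death from 6 still ties with a survivor going 5→7 (both +2), though no strict reversal remains. State whether change or score is ranked in a pooled stratum. Do not use the raw score without strata.

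Optionally, add a proportional-odds model of the score with treatment, baseline score and severity, reporting a common odds ratio with 95% confidence interval as a supportive estimate. Its cost is the proportional-odds assumption, which the van Elteren test does not need.

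Reconcile Protocol inclusion 3b with exclusion 2. In the same edit, settle which test governs: Protocol 9.4.2 plans a repeated measures analysis of variance for change variables, SAP 3.2.1 makes it exploratory, SAP section 9 does not list the switch, and SAP 8.1 states that no testing will be done.

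The statistical change needs a few lines of SAP text and code and no new data. It should be settled before the unblinded interim analysis, which includes secondary endpoints.
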